Ultrasonic (US) assessment is performed the same day as the clinical examination by one of two certified sonographers unaware of the clinical results. Grey-scale (GS) and colour Doppler (CD) US are performed for 26 joints (13 unilateral) and 12 entheses (6 unilateral) per patient using a General Electric Logiq E9 (Milwaukee, Wisconsin, USA) with a linear array matrix transducer (15 MHz frequency). All ultrasound examinations are done in longitudinal projections. Hands and feet joints are scanned from both the dorsal and plantar position, the knee scan includes medial and lateral projections, and the wrists are assessed by central, radial and ulnar scans. Images and clips are stored and will be scored by two US experts (KE, JG). For the purpose of calculating the interobserver reliability for GAUS, GSAUS, GCUS (measures explained in "Primary US variables/predictors" below), the two experts will score the same 10 patients on every US parameter as depicted in table 3s. Similarly, all scans on 10 patients will be scored twice by the same rater with a time interval of 10 days to calculate the intra-observer reliability. Before the reliability tests, five US examinations will be scored by the two experts together in order to achieve consensus.

Joints

The 26 joints include the metacarpo-phalangeal (MCP) 2-3 (dorsal and plantar), proximal interphalangeal (PIP) 2-3 (dorsal and plantar) and distal interphalangeal (DIP) 2-3 (dorsal and

plantar), the wrist (central/radial/ulnar and volar projection), the knees (medial and lateral), and metarso-phalangeal (MTP) 1-3 (dorsal), and DIP 2-3 (dorsal) of the toes. Each of the 46 projections will be semiquantitatively scored 0-3 for Grey-scale synovitis (GSS) and 0-3 for CD.[29,30]

The joint will also be assessed for erosions and osteophytes. Erosions are defined by a step-down contour defect visible in transversal and longitudinal planes (scored 0-3 with 0=no erosion, 1=erosion<2mm, 2=erosion>2mm, 3=large destruction of the joint). Osteophytes are defined by a step up contour semiquantitatively scored from 0-3 (0=no osteophyte, 1= small osteophyte, 2= medium osteophyte and 3=large and diffuse osteophytes).[31]

For GSS, CD activity, erosions and osteophytes, the score per projection will be used to calculate a total Joint (J)-GSS (range 0-138), a total (J)-CD (range 0-138), a total (J)-erosion score (range 0-138) and a total (J)-ostephytes score (range 0-138).

Tendons

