The inter- and intra-rater reliability for GAUS, GSAUS, GCUS will be quantified using the intraclass correlation coefficient (ICC).[41] ICC ranges between 0 (no reliability) and 1 (perfect reliability). Values <0.40 will be interpreted as poor reliability, 0.40 to 0.59 as fair reliability, 0.60 to 0.74 as good reliability and 0.75-1.00 as excellent reliability.[42] The ICC will be of the type ICC(2,1), i.e. based on a two-way random effects model estimating agreement with single measures.[41,43]

Treatment persistency and reasons for withdrawal

The total number and percentage of patients who continued treatment from baseline to follow-up will be reported for each pain profile (WP versus no WP). Among patients who stopped treatment during the observation period, reasons for withdrawal will be reported as either 1) adverse events or 2) lack of efficacy.

Primary analyses

The primary outcome is ACR20, coded as a binary variable. The co-primary predictors of interest are WP and GAUS, both coded as a binary variable. The primary analyses will be based on logistic regression models investigating if there is an association between ACR20 response and each of the primary predictors of interest (WP, GAUS). Furthermore, a test for interaction between GAUS and WP will be performed. Estimates will be reported from unadjusted and adjusted models, and the crude numbers of responders will be reported for each of the binary predictors. The adjusted models would ideally include all available factors that are expected to influence the result (hypothesis driven model), however, due to the relatively small sample size and risk of statistical overfitting, the models will only be adjusted for age (years) and gender (male/female). The design of the primary models is illustrated in Table 2.

Rationale for the selected confounders

Augmented pain processing seem to be more prominent in women compared to men[36,44], and it is possible that gender affects the odds of experiencing a treatment response[45-47], and hence may confound the relationship between WP pain profile (predictor) and response (outcome). Similarly, higher age may also by several pathways influence both the measures of the primary

predictors and the chance of achieving a treatment response. The primary model will not be adjusted by type of treatment received, due to risk of bias from indication for treatment.[48]

Secondary analyses

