Assessment of pain mechanisms:

Protocol: Characterization of pain profiles will be based on the following assessment tools: The PainDETECT Questionnaire (PDQ), The Widespread Pain Index (WPI), The Swollen to Tender Joint Count Ratio (SJ/TJ) and the Tender Point Count (TPC).

SAP: When elaborating the SAP, the author group (including a rheumatologist with expertise in pain) achieved consensus on defining the primary variable of pain profile as the presence of widespread, non-arthritic pain interpreted as a WPI score ≥ 4 and presence of generalised pain ($\geq 4/5$ regions). The definitions of secondary measures of augmented pain processing by PDQ, TP and SJ/TJ still adhere to the protocol.

Rationale: Definitions of primary and secondary predictors were needed to clarify the study objective and specify the statistical analyses.

Imaging:

1)Protocol: Scoring of entheses/tendons will adhere to the Madrid Sonographic Enthesitis Index (MASEI) algorithm.

SAP: The scoring of entheses will not only rely on the MASEI algorithm but also include recommendations from the OMERACT expert group; due to assessment of Doppler and bursitis.[53] All knee scans were performed with the patient in supine position. In order to visualize maximal Doppler flow the knee was scanned in fully extended position, instead of 70° flexion as proposed in the MASEI publication.[54] This might have led to a systematic bias in measures of the distal patella enthesis thickness, as the ultrasonographers reported that a large proportion of patients had a pathological thickness (>4mm) of this site (according to the MASEI scoring) without any other characteristics of enthesitis or tendinopathy. It was therefore decided not to include this score in the total subacute ultrasound score. No error was suspected in the scoring of thickness of the proximal patella entheses.

Rationale: Based on current knowledge this was considered appropriate according to the two US experts (JGM, KE).

2)Protocol: The interobserver reliability of the two sonographers will be investigated by double scans of patient 6–35. US assessment will occur on the same day as the clinical examination.

SAP: The interobserver (KE vs JGM) reliability AND intraobserver (JGM) reliability will be tested. Only 10 patients will be used for these analyses.

Rationale: The reduced number of patients used for reliability testing does not adhere to gold standards but was chosen due to feasibility reasons.

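### The reliability of the ultrasound scores is to be graded from the ICC value alone, but with 10 patients and two scorings an 'excellent' 0.75 has an interval that reaches 'poor'

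*SAP*

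**What the plan says.** Under Interobserver and intraobserver reliability, the SAP quantifies both kinds of reliability for GAUS, GSAUS and GCUS by an intraclass correlation. It specifies the form: "The ICC will be of the type ICC(2,1), i.e. based on a two-way random effects model estimating agreement with single measures". It then attaches a verbal grade to the value: "Values <0.40 will be interpreted as poor reliability, 0.40 to 0.59 as fair reliability, 0.60 to 0.74 as good reliability and 0.75-1.00 as excellent reliability". That section mentions no interval.

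The sample is set under Ultrasonic assessments. For inter-observer reliability, "the two experts will score the same 10 patients on every US parameter as depicted in table 3s". For intra-observer reliability, "all scans on 10 patients will be scored twice by the same rater with a time interval of 10 days". What is scored is recorded material: "Images and clips are stored and will be scored by two US experts".

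Protocol deviations, Imaging, item 2, gives the history. The protocol had planned double scans of patients 6 to 35 to compare the two sonographers. The SAP now says "Only 10 patients will be used for these analyses" and concedes: "The reduced number of patients used for reliability testing does not adhere to gold standards but was chosen due to feasibility reasons".

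**The concern.** A four-band scale with bands 0.15 to 0.25 wide above 0.40 needs an estimate that is reasonably precise on that scale. Ten patients with two scorings do not give one. If the rule is followed as written, each score receives one word, and the reader cannot see that neighbouring grades, or all four, fit the data equally well.

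The label matters because GAUS is a co-primary predictor and GSAUS and GCUS are secondary predictors. Readers will use the reliability statement when they judge how far to trust the ultrasound results.

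There is a second, smaller point. Each patient is scanned by one of two sonographers. Double scanning would have captured differences in how they obtain images; scoring the same stored images twice cannot. The stated rationale covers the smaller number of patients but not this change in what is measured.

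**Working it through.** **Inputs from the SAP.** n = 10 patients; k = 2 scorings; ICC(2,1); bands cut at 0.40, 0.60 and 0.75. The SAP gives no precision figure for the ICC, so there is none to reproduce.

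**Assumptions.** Two-sided 95% interval (the SAP sets no level for the ICC). The ratio of rater to error mean square, MSC/MSE, is not given. It is set to 1 (no systematic difference between scorings) and then varied from 0.01 to 5.

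**Step 1: simple F interval (ICC(3,1) form, which needs only the observed value r).**
- F = (1 + r)/(1 − r) = 1.75/0.25 = 7.
- F(0.975; 9, 9) = 4.03.
- Lower: 7/4.03 = 1.74, so (1.74 − 1)/(1.74 + 1) = 0.27.
- Upper: 7 × 4.03 = 28.2, so (28.2 − 1)/(28.2 + 1) = 0.93.

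**Step 2: interval for the ICC(2,1) that the SAP specifies, r = 0.75, MSE = MSC = 1, hence MSR = 7.**
- a = kr/[n(1 − r)] = 1.5/2.5 = 0.6; b = 1 + kr(n − 1)/[n(1 − r)] = 1 + 13.5/2.5 = 6.4.
- Satterthwaite df = (a + b)²/(a²/1 + b²/9) = 49/4.91 = 9.98.
- F(0.975; 9, 9.98) = 3.78; F(0.975; 9.98, 9) = 3.97.
- Lower = n(MSR − 3.78)/[3.78(k + kn − k − n) + n·MSR] = 32.2/(37.8 + 70) = 0.30.
- Upper = n(3.97·MSR − 1)/[(k + kn − k − n) + n·3.97·MSR] = 267.9/287.9 = 0.93.

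**Step 3: sensitivity.** With MSC/MSE from 0.01 to 5 the lower limit at r = 0.75 lies between 0.23 and 0.31. ICC(1,1) gives 0.30 to 0.93 and Fisher z 0.29 to 0.93. A 90% ICC(3,1) interval gives 0.38 to 0.91. Every lower limit is below 0.40.

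**Step 4: other observed values (ICC(2,1), MSC/MSE = 1).**

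| Observed ICC | SAP grade | 95% interval | Grades covered |
|---|---|---|---|
| 0.40 | fair | −0.24 to 0.81 | poor to excellent |
| 0.60 | good | 0.03 to 0.88 | poor to excellent |
| 0.75 | excellent | 0.30 to 0.93 | poor to excellent |
| 0.80 | excellent | 0.41 to 0.95 | fair to excellent |
| 0.85 | excellent | 0.53 to 0.96 | fair to excellent |
| 0.90 | excellent | 0.67 to 0.97 | good to excellent |
| 0.95 | excellent | 0.82 to 0.99 | excellent |

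The lower limit passes 0.40 at an observed ICC of about 0.80, 0.60 at about 0.88 and 0.75 at about 0.93. Over the range of MSC/MSE tried, the first threshold runs from 0.80 to 0.84 and the last from 0.93 to 0.95.

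**Step 5: how often the rule gives each grade (simulated, n = 10, k = 2, no rater effect).** A true ICC of 0.59 (fair) is graded excellent in about 18% of samples and poor in about 23%. A true 0.75 is graded excellent in about 49% and poor in about 6%.

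**Step 6: the planned number, for comparison.** Patients 6 to 35 are 35 − 6 + 1 = 30. With 30, an observed 0.75 has an interval of about 0.54 to 0.87, which excludes poor but not fair.

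**Step 7: the obvious alternative rule.** Grading by the lower 95% limit (Step 1 form) at n = 10 would call a true 0.75 poor in about 67% of samples and a true 0.85 poor in about 35%.

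**The case against.** **An interval may already be planned.** Table 3s is cited for exactly this analysis and is not in the text at hand. The comparison and model tables that are shown all have a 95% interval column, so one in Table 3s cannot be ruled out. This stands. The point is therefore limited to the section text, which ties the grade to the ICC value and would still do so if the table carried an interval.

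**The small number is disclosed.** This also stands. The SAP lists it as a deviation and gives a reason. The defect is a sharp grading rule that this number cannot support.

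**0.75 is the edge of the top band.** True, and an observed value of 0.93 or more would support the top grade even with 10 patients. But estimates graded fair or good, and those at the bottom of excellent, are not resolved.

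**Stored-image reading is visible in the SAP.** It is, and the SAP speaks of rater reliability. Naming it in the result is a clarification.

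Three stronger readings are tempting, and the document supports none of them. A reader might infer that an unsupported grade has been reported; none has, and this is a planned rule. A reader might infer that a high grade will be used to argue that ultrasound has no prognostic value; the SAP does not say so and makes nothing conditional on the ICC. A reader might infer that a better ICC statement would show whether measurement error explains a null odds ratio. It would not, because GAUS enters the model as zero versus above zero and the other two scores as median splits. An ICC on the total scores does not measure misclassification at those cuts.

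**Conclusion.** The point holds as a minor one. With 10 patients and two scorings, grading the ICC value alone yields labels that the data cannot separate. An observed 0.75, labelled excellent, has a 95% interval of about 0.30 to 0.93. Poor is excluded only from about 0.80, and excellent is supported only from about 0.93.

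These figures assume a 95% level and, for the central values, no systematic difference between scorings. The conclusion for 0.75 is the same under every ICC form and rater ratio tried. Whether Table 3s adds an interval is unknown. The description should also make clear that acquisition differences between the two sonographers are not part of what is measured. The reliability analysis is supporting, and the ACR20 models are unaffected.

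**What to change.** In Interobserver and intraobserver reliability, state that each ICC(2,1) is reported with its 95% confidence interval, and replace the single grade by the range of grades the interval covers (for example, an ICC of 0.75 with an interval of 0.30 to 0.93, poor to excellent). Make sure Table 3s has the matching column. Do not grade by the lower limit alone: at this sample size it would label many reliable scores poor.

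Describe the result as inter- and intra-reader reliability on stored images, and say that differences in image acquisition between sonographers are not assessed.

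The cost is a few lines of wording. No new data are needed, and the interval comes from the same analysis of variance as the ICC. The reliability statement will read less favourably.

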The current study will include prospectively collected data on patients with PsA treated in routine care who initiate a conventional synthetic- or biologic – disease modifying (cs/bDMARD) treatment due to active PsA.

Analysis objectives

Our overall scientific objective is to investigate pain profile in relation to arthritic US findings in patients with PsA, and to study the predictive value of pain profile and ultrasonographic scores on response to conventional synthetic or biologic disease modifying (cs/bDMARD) treatment.

Population

The study is designed as an exploratory, prospective observational study enrolling patients with PsA according to CASPAR criteria,[21] who initiate/switch b/csDMARDs in routine care due to active PsA. Patients complete an examination programme at baseline and after 4 months including interview, clinical, ultrasonic and para-clinical assessments as well as electronic questionnaires. The inclusion period was between 17th of September 2015 and 1st of June 2017. A flow chart (figure 1) depicts the eligibility and inclusion process.

Collected variables

Interview

Baseline

A physician (PH or CB) interviews patients regarding their PsA and psoriasis diagnoses, current and former medical treatments, demographic and lifestyle factors and known co-morbidities (physical and mental) according to the pre-specified protocol.[1] Variables of interest for are depicted in Table 1.

Follow-up

At follow-up the same physicians (PH or CB) register changes in medical treatments including reasons for withdrawal of cs/bDMARDs.

Patient reported outcome measures (PROMs)

Touchscreen questionnaires are used for completing PROMs at baseline (Table 1) and at follow-up.

The intensity of pain is assessed by a visual analogue scale (VAS) (0-100 mm). The WPI and PDQ are applied to assess the patient's pain profile; WPI[12] is applied to determines if the pain is widespread or not, and the PDQ[14,22] clarifies if nociceptive or neuropathic pain features are dominating. These measures are described in more details in a later section.

Four other disease related concepts are covered by PROMs (Table 1):

- Health related quality of life/disease impact is assessed by The Psoriatic Arthritis Impact of Disease (PsAID)[4] and the Dermatology Life Quality Index (DLQI).[23]
- Mental well-being/anxiety is assessed by Generalized anxiety disorder (GAD-10)[24] and the Medical Outcome Survey Short Form-36 mental health score (MOS SF-36 MH).[25]

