These will include measures of global subacute ultrasonic score (GSAUS) and the global chronic ultrasonic score (GCUS) as binary variables where the median value will be the cut-off defining patients with high versus low levels of GSAUS and GCUS pathology, respectively.

The GSAUS (range 0-204) will be calculated as the sum of Joint (J)-GSS (range 0-138) + (T)-GSS (range 0-32) + (E)-Structure (range 0-12) + (E)-Thickening (range 0-10) + (E)-Bursitis (range 0-12). It was decided not to include the thickness of the distal patella enthesis when calculating the GSAUS as explained in the “protocol deviations” section below.

The GCUS (range 0-312) will be calculated as the sum of (J)-erosion (range 0-138) + (J)-osteophytes score (range 0-138) + (E)-Calcification (range 0-36).

Primary pain profile variable/ predictor

Inspired by the revised 2016 diagnostic criteria for fibromyalgia[12], we will define a widespread pain profile as having pain in at least 4 of 5 predefined body regions (generalized pain criterion) in addition to having a WPI ≥ 4 . The WPI consist of 19 body parts supported by an explanatory body diagram, and patients indicate the body areas in which they have experienced pain during the last week, resulting in a score between 0 and 19. Patients are carefully instructed not to consider joint pain when completing the WPI. All the WPI body parts except the jaw, chest and abdomen are listed within one of the 5 predefined body regions as described by Wolfe et al.[12]

Secondary pain profile variables/predictors

Augmented pain processing will also be explored in secondary analyses by the TPC, a swollen/tender joint ratio (SJ/TJ) and the PDQ score.

While a TPC ≥ 11 (in addition to chronic widespread pain) indicates fibromyalgia (FM) according to the old (1990) FM criteria[13], an Italian study[34] found a TPC ≥ 8 to discriminate between FM and PsA (sensitivity 93% and specificity 82%). We will explore this cut-off as indicator of widespread, non-arthritic allodynia in the present study.

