Secondary analyses will include repeating the logistic regression models using the secondary outcomes (MDA, DAPSA 50% and PR improvement) for the primary predictors (WP and GAUS, both binary), as well as repeating the logistic regression model with ACR20 as outcome for the secondary predictors of interest (binary measures of PDQ, TPC, SJ/TJ GSAUS and GCUS). The number of responders (and corresponding percentage) will be reported for every predictor (all categorical). Furthermore, change in the domains of the updated OMERACT core outcome set according to WP and GAUS profile will be analysed, and scatter diagrams will be applied to study the relationship between continuous measures of WPI and GAUS at baseline and the change in DAS28-CRP and in DAPSA during the treatment period.

Handling of multiplicity and other data conventions

In all analyses, p-values < 0.05 will be considered statistically significant. No correction for multiple testing will be done; instead the results will be interpreted with caution in the context multiplicity.

Missing data and analysis population

The main analysis population will be defined as those who fulfilled the inclusion criteria (i.e. the intention-to-treat population). For the outcomes (follow-up visit), missing data will be imputed by a non-responder assumption (i.e. baseline observation carried forward).

An as-observed population will be defined as those for whom data have been observed and no imputation will be carried out.

A per-protocol population will be defined as those who have complete data on the variables used for the analysis (i.e. the response variable and the predictor variables) and who adhered to the assigned treatment during the observation period.

Sensitivity analyses

A sensitivity analysis will be conducted to study the value of the primary pain and ultrasound predictors on ACR20 response including the per-protocol population and as-observed population.

Programming

The analyses will be conducted using the statistical program R (version 3.3.3).[49]

The program code for the primary analyses in the statistical program R:

```

#Logistic regression, ACR20 response, WP, univariate
M1<-glm(ACR_response ~ WP, family=binomial)
anova(M1, test="Chisq")
summary(M1)

#Logistic regression, ACR20 response, WP, adjusted for gender and age
M1<-glm(ACR_response ~ WP + Gender + Age, family=binomial)
M1<-glm(ACR_response ~ Gender + Age, family=binomial)
anova(M1,M0, test="Chisq")
summary(M1)

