Table 3: Prognostic value of US and widespread pain profile on secondary outcomes

Predictors	n	n response (%)	Simple logistic regression		Multivariable, adjusted for age and gender	
			OR (95%CI)	P-value	OR (95%CI)	P-value
MDA						
Pain profile						
WP+			[Reference level]		[Reference level]	
WP-						
US profile						
GAUS =0						
GAUS >0			[Reference level]		[Reference level]	
DAPSA 50%						
Pain profile						
WP+			[Reference level]		[Reference level]	
WP-						
US profile						
GAUS =0						
GAUS >0			[Reference level]		[Reference level]	
PR-improvement						
Pain profile						
WP+			[Reference level]		[Reference level]	
WP-						
US profile						
GAUS =0						
GAUS >0			[Reference level]		[Reference level]	

GAUS, Global Acute Ultrasonic Score; WP; widespread pain; MDA, Minimal disease activity; DAPSA, Disease Activity Index for Psoriatic arthritis; PR-improvement; Patient reported improvement.

Figure 2: Scatter diagrams: Association between change in DAPSA and DAS28-CRP and baseline WPI and GAUS scores

- a) WPI score vs Δ DAPSA
- b) WPI score vs Δ DAS28
- c) GAUS vs Δ DAPSA
- d) GAUS vs Δ DAS28

Table 4: Change in the OMERACT PsA core set domains* from baseline to follow-up (ITT population)

PsA Core domains	All patients		Difference (95% CI)	P-value	GAUS=0	GAUS>0	Difference (95% CI)	P-value
	WP-	WP+						
MSK disease activity								
Δ SJC								
Δ TJC								
Δ SPARCC								
Δ BASDAI								
Skin disease								
Δ PASI								
Pain								
Δ VAS pain								
Δ SF-36 BP								
Physical Function								
Δ SF-36 PF								
Δ HAQ								
Δ BASFI								
HRQol								
Δ DLQI								
Δ PsAID								
Patient Global								
Δ Patient Global VAS								
Fatigue								
Δ NRS Fatigue								
Δ SF-36 VT								
Systemic inflammation								
Δ CRP								

*OMERACT PsA core domains set as updated and endorsed in 2016[3]

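### Table 4 tests raw change by WP and GAUS group without the baseline value, so regression to the mean can distort its exploratory prognostic reading

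*SAP*

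**What the plan says.** The Secondary analyses section of the SAP states that "change in the domains of the updated OMERACT core outcome set according to WP and GAUS profile will be analysed". It names no model, test or covariate. The Table 4 shell (headed "Change in the OMERACT PsA core set domains* from baseline to follow-up (ITT population") lists 16 change scores. Each has one difference with a 95% CI and one P-value for WP- versus WP+, and the same again for GAUS=0 versus GAUS>0. It shows no baseline values and no adjusted column. Tables 2 and 3 do have an adjusted column, but the Primary analyses section limits the covariates there ("the models will only be adjusted for age (years) and gender (male/female"). The section on multiplicity counts p<0.05 as significant in every analysis, without correction.

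On timing, the Population section says "Patients complete an examination programme at baseline and after 4 months". For the WPI, "patients indicate the body areas in which they have experienced pain during the last week". For GAUS, "Ultrasonic (US) assessment is performed the same day as the clinical examination". Both groupings therefore come from the programme that supplies the starting value of every change score.

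Figure 2 is a separate, graphical item: "scatter diagrams will be applied to study the relationship between continuous measures of WPI and GAUS at baseline and the change in DAS28-CRP". DAPSA is plotted in the same way. The section on endpoints classes all these change outcomes as exploratory, although their analysis appears under Secondary analyses.

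**The concern.** Change contains the baseline value with a minus sign. A score that is unusually bad on the baseline day tends to be less bad four months later, whatever the treatment does. If the variable that forms the groups picks up the same day-to-day or week-to-week fluctuation, the group that starts worse will improve more on average, even with no prognostic information in the grouping. Patients enter because treatment is started or switched for active disease, a time when such fluctuation is plausible.

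The overlap is most plausible for VAS pain, SF-36 bodily pain, patient global and tender joint count with WP, and for swollen joint count and CRP with GAUS. It is weaker for PASI or DLQI.

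The study asks whether pain profile and ultrasound findings predict response. If WP+ patients start worse, the artefact works in their favour and can hide or reverse a poorer response. If GAUS>0 patients start worse, it can imitate a better response. Table 4 gives no second estimate against which to judge this.

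**Working it through.** **1. Inputs.** From the SAP: 16 measures × 2 groupings = 32 comparisons, with groupings and starting values from the same baseline programme. The SAP gives no sample size, SD, baseline to follow-up correlation (rho) or expected change, so there is no planned figure to reproduce. Assumed here: rho 0.4 to 0.7; equal SD at both visits; no true prognostic effect; follow-up observed (patients with baseline carried forward contribute zero change).

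**2. Grouping follows the observed baseline score.** Expected follow-up is a constant plus rho × baseline. The groups then differ by rho × gap at follow-up, and in change by

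rho × gap - gap = -(1 - rho) × gap.

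- 10-point gap: (1 - 0.7) × 10 = 3 points, up to (1 - 0.4) × 10 = 6 points.
- 20-point gap: 6 to 12 points.
- Illustration on VAS pain, assuming SD 22 mm, 35% WP+ and a correlation of 0.5 between the variable behind the grouping and baseline pain: gap = 0.5 × 22 × 0.370/(0.35 × 0.65) = 17.9 mm. The spurious difference is then about 11, 9 or 7 mm at rho 0.4, 0.5 or 0.6.

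**3. Grouping follows only the stable part of the score.** The whole gap persists at follow-up, so the expected difference in raw change is gap - gap = 0.

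Between cases 2 and 3 the error is at most (1 - rho) × gap. Only a grouping tied more closely to the transient part than the observed score itself would exceed that, and this point does not rely on such a case.

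**4. False-positive rates.** Simulation with no true effect: N = 100, 35% in the WP+ group, rho = 0.5, nominal 5%, 1,500 simulated studies per setting. All inputs are assumed.

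| Baseline gap (SD) | Case 2: raw change | Case 2: baseline-adjusted | Case 3: raw change | Case 3: baseline-adjusted |
|---|---|---|---|---|
| about 0.16 | 0.064 | 0.043 | 0.059 | 0.086 |
| about 0.49 | 0.209 | 0.045 | 0.057 | 0.285 |
| about 0.81 | 0.499 | 0.051 | 0.056 | 0.683 |

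Over the full range tried (N 60 or 100, rho 0.4 to 0.7), case 2 gave 5% to 60% for raw change and 4% to 6% after adjustment. Case 3 gave 4% to 6% for raw change and 5% to 78% after adjustment.

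**5. Why both columns are needed.** With b the within-group slope of follow-up on baseline, adjusted difference - raw difference = (1 - b) × gap. At the largest gap in the table, case 2 gives a raw difference of -0.41 SD and an adjusted one near 0. Case 3 gives a raw difference near 0 and an adjusted one of +0.48 SD. The raw error favours the worse-starting group and the adjusted error goes against it. A finding that survives both is therefore robust to which case applies.

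**The case against.** Several points on the other side stand.

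- **The distortion is conditional.** A reader might infer that Table 4 is bound to show a false prognostic effect. The documents do not support that. The SAP's introduction presents widespread pain as sensitization that outlives joint disease activity, and patients are told to leave joint pain out of the WPI. Both point towards a stable trait. The one-week recall points the other way, so the question is open. For GAUS, sonographers do not know the clinical results, which limits shared rater error but not a shared flare. The SAP itself cites discrepancies between ultrasound and clinical measures, so a worse start in GAUS>0 is an expectation and not a documented fact.
- **Baseline adjustment is not a cure.** A reader might conclude that ANCOVA should replace raw change. These groups are not randomised, and case 3 shows that adjustment can create a difference (Lord's paradox). In the illustration in step 2, ANCOVA returns zero only because no effect given baseline was assumed, so this is no evidence in its favour.
- **Figure 2 is not a group comparison.** It plots continuous scores, with no groups and no test. The same artefact can tilt the cloud of points, but no inference is planned from it.
- **Imbalance is largely visible.** Tables 1 and 1s report baseline values by the same groups for 13 of the 16 measures (not SF-36 bodily pain, physical function or vitality). This informs the reader but does not change the Table 4 estimates or P-values.
- **The outcomes are exploratory.** The SAP also promises caution, though only about multiplicity. The primary ACR20 models are outside this point.

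What remains is that Table 4 still makes 32 significance tests on raw change with an open method and no adjusted estimate.

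**Conclusion.** The point holds for Table 4 in conditional form. Raw change is tested between groups formed at the baseline visit without the baseline value, and without even the age and gender adjustment used in Tables 2 and 3. Regression to the mean can add a spurious difference between zero (stable trait) and about (1 - rho) × the baseline gap (grouping follows the observed score). These sizes rest on assumed gaps and correlations, equal variances at the two visits and no true effect; the SAP supplies none of these values. For small gaps the effect is negligible: about 6% rejection at 0.16 SD in the setting tabulated above.

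Severity is minor to moderate, because the outcomes are exploratory but bear directly on the prognostic question. Figure 2 warrants a caution only.

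**What to change.** - **Table 4:** keep the raw difference and add an adjusted column from a model of change (or follow-up value) on group, baseline value of that measure, age and gender. Show baseline values per group, which also covers the three SF-36 scales missing from Tables 1 and 1s.
- **Secondary analyses text:** name both models now. State in advance that a prognostic reading needs the raw and adjusted columns to agree, and that disagreement will be reported as unresolved, because adjustment can itself mislead in non-randomised groups.
- **Figure 2:** add a caution to the legend, or a supplementary regression of change on WPI (or GAUS) that includes the baseline DAPSA or DAS28-CRP score.

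The cost is a few lines of SAP text, one more column and modest extra analysis; the data needed are the baseline values from which change is already computed. The downside is that an exploratory result may look less clear-cut.
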